Our transdisciplinary team, consisting of national experts in post-stroke aerobic exercise & gait rehabilitation, neurologists focused on stroke recovery, an exercise physiologist, a cardiologist and a biostatistician, has developed a novel training protocol that safely enables persons with chronic stroke to achieve vigorous intensity in the first session (a mean 76% heart rate reserve).¹² Based on the well-tested exercise science and cardiac rehabilitation strategy of high-intensity interval training (HIT), this protocol uses bursts of maximum speed walking with alternating recovery periods, to sustain higher aerobic intensities than physiologically possible with continuous exercise,¹³ and with lower perceived exertion.¹⁴ Our preliminary data demonstrate that this innovative locomotor HIT protocol can elicit >40% increases in walking capacity, gait speed and aerobic fitness in just 4 weeks. However, no previous studies have compared HIT with the current best-practice model post-stroke (MAT). Further, it is possible that the longer 12 week HIT durations tested in some heart disease studies might yield even better outcomes, approaching normal walking capacity, but this has not been tested.

The **objective of this proposal** is to determine the optimal training intensity and the minimum training duration needed to maximize immediate improvements in walking capacity in chronic stroke. We propose a single-blind 3-site RCT. Fifty persons >6 months post stroke will randomize to either 12 weeks of HIT or 12 weeks of MAT; each for 45 minutes, 3x/week. Clinical measures of walking function, aerobic fitness, daily walking activity and quality of life will be assessed at baseline (PRE) and after 4, 8 and 12 weeks of training (4WK, 8WK, 12WK).

Aim 1: Determine the optimal locomotor training *intensity* for eliciting immediate improvements in walking capacity among chronic stroke survivors. *Primary study hypothesis:* Compared with 4 weeks of MAT, 4 weeks of HIT will elicit significantly greater improvement in walking capacity, as measured by change in the 6-minute walk test from PRE to 4WK. This aim is powered for proof of concept that vigorous training intensity is a 'critical ingredient' for post-stroke locomotor recovery.

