The proposed study builds on our previous work and overcomes the limited scientific rigor of previous studies with a high-quality, moderately-sized, 3-site RCT, using our novel HIT protocol to ensure vigorous training intensity and a best-practice MAT control group. This study will determine the optimal training intensity and minimum training duration needed to maximize immediate improvements in walking capacity and other measures (gait speed, aerobic fitness, metabolic cost of gait, daily walking activity and quality of life) among chronic stroke survivors. This will be the first study designed to compare HIT and MAT in chronic stroke and the first study in any population to compare different HIT durations. Aim 1 is expected to provide proof of concept that vigorous training intensity is a 'critical ingredient' for locomotor recovery, by showing that HIT elicits significantly greater immediate improvement in walking capacity compared with MAT, using a clinically feasible 4-week training dose. Aim 2 is expected to show that longer durations of HIT elicit continued significant improvements, approaching normal walking capacity, with increasing benefit over MAT across 12 weeks of training. However, if effects peak earlier than 12 weeks, it would provide scientific justification to keep testing a shorter protocol that is more aligned with patient preferences and current reimbursement models.

[figure not shown]

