Outcome testing will be administered by licensed physical therapists or physical therapist assistants who are blinded to group randomization. Testing will occur before intervention (PRE) and after approximately 4, 8 and 12 weeks of training (4WK [*primary endpoint*], 8WK, 12WK). Each testing session will last approximately 2 hours and may include the following measures:

- Walking capacity testing (*6-minute walk test, primary outcome measure*) involves walking back and forth around two cones, using assistive devices, orthotics, guarding and rest breaks as needed.¹⁴⁸ The distance that the participant is able to walk in six minutes is recorded.
- Walking speed testing (*10-meter walk test*) will be performed with a stopwatch and/or a commercially available electronic walkway.^{146,147} Participants will walk down a hallway and/or electronic walkway, using assistive devices, orthotics and guarding as needed. Each test may be performed twice at comfortable speed and twice as fast as possible.
- Aerobic capacity testing involves respiratory gas measurement (VO₂ and VCO₂) by having the participant breathe through a facemask during an exercise test. This testing will use the same exercise protocol as the stress test above and may be performed simultaneously with the stress test. Peak aerobic capacity is defined as the highest VO₂ measurement achieved during the test. After finishing this test and a rest period, participants may complete a verification phase to help determine whether maximum physiologic capacity (a true VO₂-max) was reached.¹⁵¹ During this verification phase, the participant would be asked to walk as fast as possible for approximately 3 minutes. The treadmill screening test may be repeated at each testing time point to inform speed selection for aerobic capacity testing.
- The metabolic cost of gait is measured by the oxygen consumption rate (VO₂) during gait, with adjustment for walking speed and resting VO₂.⁷⁹ The metabolic cost of gait will be assessed with treadmill walking at approximately the average speed recorded during the 6-minute walk test.
- Daily walking activity assessment involves wearing an activity monitor continuously during waking hours for ≥ 3 days and possibly recording sleep/wake times.¹⁵²⁻¹⁵⁵ The monitor will be worn on the non-paretic leg.

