- The Stroke and Aphasia Quality of Life Scale,^{157,158} Stroke Impact Scale,¹³⁸ EQ-5D and Patient Health Questionnaire¹⁴⁷ are reliable and valid self-report quantitative surveys that include questions about quality of life. One or more of these questionnaires will be used.
- The Global Rating of Change (GROC)¹⁵⁹ is a questionnaire that assesses overall impressions of change in health status from the perspective of the participant. The GROC is a 15 point ordinal scale with -7 indicating "a very great deal worse," 0 indicating "no change," and +7 indicating "a very great deal better". The GROC is not applicable at baseline testing because it measures change only.

Heart rate data may also be recorded during the above testing. If there are any issues with data capture (e.g. equipment malfunction), it is possible that participants could be asked to repeat individual tests as long as it would still be possible to obtain quality data without increasing risk to the participant.

Randomization

Participants will be enrolled after PRE testing and randomized to either HIT or MAT. Randomization will be stratified by site and by baseline walking speed (<0.4 , ≥ 0.4 m/s), to help ensure that groups are balanced within sites and on this critical prognostic factor.^{149,150} Within each stratum, we will randomize in *block sizes of 2 or 4*. Block size will be *randomly permuted* to prevent personnel from being able to predict the last randomization within a block.

Training Intervention Protocols

Common features between protocols. Participants in both groups will be asked to perform 36 training sessions over approximately 12 weeks, with repeated outcome testing after each [12 session / 4 week] block. Target training frequency will be 3 sessions per week. Both groups will train for approximately 45 minutes per session, v.5, 16Mar2021

using orthotic & assistive devices and handrail balance support on the treadmill as needed.¹⁴⁴ Each session will include a 3 minute warm up, 10 min overground training with guarding from a physical therapist, 20 min treadmill training wearing a harness for fall protection, another 10 min overground training and a 2 min cool down. Target heart rates (HRs) will be based on the peak HR from exercise testing, to account for β -blocker medications.¹⁴⁴

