H_{1a} will be tested by the significance of the [group x time] contrast from Baseline to POST-4wk for the 6-minute walk test at $\alpha=0.05$. For H_{1b}, secondary outcomes will be tested separately using the same model as H_{1a} to identify the most sensitive measures to carry forward into future studies.¹¹⁰ The Benjamini-Hochberg procedure²²³ will be used to control the false discovery rate (FDR) for the secondary outcomes.

Aim 2: Determine the minimum locomotor training duration needed to maximize immediate effects

Hypothesis 2a (H_{2a}): Within the HIT group, *walking capacity* (6 minute walk test distance) and *secondary outcomes* will significantly increase from 4WK to 8WK and from 8WK to 12WK

Hypothesis 2b (H_{2b}): Compared to MAT, HIT will elicit significantly greater improvements in *walking capacity* and *secondary outcomes* from PRE to 8WK and from PRE to 12WK

H_{2a} will be tested by the significance of the respective time contrasts within the HIT group. **H_{2b}** will be tested by the significance of the respective [group x time] contrasts. Secondary outcomes will have FDR control.²²³

Data and Safety Monitoring Plan

An adverse event (AE) is an undesired medical occurrence in a participant who is undergoing study procedures and does not necessarily have a causal relationship with the treatment or study procedures. This includes any adverse clinical change that occurs at any time following consent. A serious AE (SAE) is any adverse experience occurring during study participation that results in any of the following outcomes: death; a life threatening situation; inpatient hospitalization or prolongation of existing hospitalization; a persistent or significant disability/incapacity.^{209,210} The data and safety monitoring plan for this study will include participant monitoring for AEs and other problems, review of AEs and other problems by the study team and IRB, and an independent data safety monitoring board (DSMB).

Participant safety monitoring

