Hypothesis 2: To test the hypothesis that, compared with 4 and 8 weeks of HIT, 12 weeks of HIT will elicit significantly greater improvements in walking capacity and increased benefit over MAT, the same general linear model described above will be used. The hypothesis that 12 weeks of HIT will elicit greater improvements in primary and secondary outcomes compared to 4 and 8 weeks of HIT will be tested by the significance of the respective time contrasts within the HIT group. The hypothesis that HIT will elicit significantly greater improvements in primary and secondary outcomes from PRE to 8-WK and PRE to POST compared to MAT will be tested by the significance of the respective [group x time] contrasts. False discovery rate control will be applied for secondary outcomes.³

Prognostic Factor Testing

We will also test for baseline cofactors that may influence a stroke survivor's response to the interventions in this study. To do this, we will utilize a multivariate prognostic model that includes comfortable gait speed, lower extremity Fugl-Meyer motor scores, and scores on the Activities-Specific Balance Confidence Scale. These measures were selected based on previous studies suggesting that comfortable gait speed,⁴⁻⁹ lower limb Fugl-Meyer motor scores,⁹⁻¹¹ and balance abilities¹² may influence response to gait rehabilitation interventions in individuals with chronic stroke. Other potential cofactors will also be explored to inform future studies.

Safety Data Analysis

We expect a similar rate of non-serious adverse events (AEs) between HIT and MAT (e.g. temporary exercise-related soreness and fatigue), without any study-related serious AEs. In the unexpected event of one or more serious adverse events (SAE), the SAE rate will be compared between groups to confirm that there is no significant difference in major safety risk between HIT and MAT. A logistic regression model will be used for this analysis with SAE (yes/no) as the dependent variable and fixed effects for group, site, and baseline gait speed category. If there are SAE(s) in one group only, a continuity correction (0.5 SAEs added to each group) will still allow the odds ratio to be calculated.¹³

References

2. Dobkin BH. Progressive Staging of Pilot Studies to Improve Phase III Trials for Motor Interventions. *Neurorehabil Neural Repair*. 2009;23(3):197-206.

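### Aim 2 sets 12 weeks of HIT against 4 and 8 weeks only through uncontrolled changes within the HIT arm, and no named contrast tests whether the advantage over MAT grows after week 4

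*Protocol*

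**What the plan says.** Protocol, A. Specific Aims: participants "will randomize to either 12 weeks of HIT or 12 weeks of MAT". Nobody is assigned to a shorter course. Aim 2 seeks the minimum duration needed to maximise improvement. Its hypothesis has two limbs: 12 weeks of HIT does better than 4 and 8 weeks, and the benefit over MAT increases.

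Protocol, B. Background and Significance, calls the trial "the first study in any population to compare different HIT durations" and expects the benefit over MAT to increase across 12 weeks.

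Protocol, Training Intervention Protocols: both arms are asked for "36 training sessions over approximately 12 weeks, with repeated outcome testing after each" block. Under Blinded Outcome Testing, the 6-minute walk test (6MWT) entry says "The distance that the participant is able to walk in six minutes is recorded". Neither document, as available, describes a practice walk or an allowance for repeat testing.

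Protocol, Hypothesis Testing, Aim 2:
- H2a: within HIT, outcomes "will significantly increase from 4WK to 8WK and from 8WK to 12WK". This "will be tested by the significance of the respective time contrasts within the HIT group".
- H2b: HIT is compared with MAT from PRE to 8WK and from PRE to 12WK by group-by-time contrasts.

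The SAP (Hypothesis 2) keeps this structure. The advantage of 12 weeks "compared to 4 and 8 weeks of HIT will be tested by the significance of the respective time contrasts within the HIT group". Greater improvement "from PRE to 8-WK and PRE to POST compared to MAT will be tested by the significance of the respective [group x time] contrasts".

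**The concern.** The same people tested after 4, 8 and 12 weeks of one programme give a time course, not a comparison of assigned durations. A rise between two visits in the HIT arm combines the effect of four more weeks of training with anything else that changes between visits: familiarity with an effort-dependent test, encouragement, or time. H2a cannot separate these.

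The randomised MAT arm is tested at the same visits and could remove whatever the two arms share, but Aim 2 uses it only for changes measured from PRE. Such a change carries the first four weeks with it, so it cannot show whether the advantage grew later. H2a and H2b could both be positive although weeks 5 to 12 of HIT added nothing over MAT.

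The aims are meant to guide dosing of training duration in future studies and practice, and a peak before 12 weeks is to justify further testing of a shorter protocol. A repeat-test gain would hide such a peak and favour the longer programme.

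**Working it through.** **1. What each contrast estimates.** Let T be the training effect over an interval in an arm, and R any other change over that interval, assumed equal in both arms.

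| Contrast | Estimates | In the plan? |
|---|---|---|
| H2a: HIT change, 4WK to 8WK or 8WK to 12WK | T(HIT) + R | yes |
| H2b: HIT minus MAT, PRE to 8WK or PRE to 12WK | T(HIT) − T(MAT) since PRE | yes |
| HIT minus MAT, 4WK to 8WK or 8WK to 12WK | T(HIT) − T(MAT) in that block | no |

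Only the third row tests growth of the advantage after 4WK. The SAP pairs 12 weeks with 4 and with 8 weeks, whereas the Protocol uses successive blocks. Both are within-HIT contrasts, so the point is the same.

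**2. The plan's own figure.** Protocol, Sample Size: 20 m difference, two-sided 0.05, 20 per group, at least 80% power. No SD is printed, so 40 cannot be rebuilt forwards. Solving backwards:
- Normal approximation: SD = 20 / [(1.96 + 0.84) × √(2/20)] = 22.6 m.
- Noncentral t: 22.0 m.

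The 22 m used below is an inferred change SD. The plan's repeated-measures calculation may rest on something else, so 40 m is shown as well.

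**3. H2a with no training gain in the block.** SE = 22/√20 = 4.92 m. With 38 df, an observed rise of about 2.02 × 4.92 = 10 m is significant. The repeat-test gain is assumed:

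| Assumed gain per interval | SD 22 m | SD 40 m |
|---|---|---|
| 0 m | 2.5% | 2.5% |
| 3 m | 8.6% | 5.1% |
| 5 m | 16.6% | 7.9% |
| 10 m | 50.9% | 19.2% |

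Entries are the chance of a significant increase in one interval. With 19 df the SD 22 m column becomes 8.4%, 16.0% and 48.8% for 3, 5 and 10 m.

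**4. The planning values.** MAT is expected to gain 15 m per 4 weeks and HIT 35 m. So 15/35 = 43% of the planned HIT block change is not specific to HIT, with training and any repeat-test gain mixed.

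**5. H2b when the advantage stops growing.** Suppose HIT leads by 20 m at 4WK and gains nothing more over MAT. PRE to 12WK is still a 20 m difference. With 20 per arm it is significant about 80% of the time at SD 22 m and 54% at SD 30 m.

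**6. The missing contrast.** SE = 22 × √(2/20) = 6.96 m, which is √2 = 1.41 times the within-HIT SE. An equal gain in both arms cancels and the two-sided error stays at 5%. If HIT gains 20 m more than MAT in a block (35 − 15), power with 20 per arm is 98% at SD 15 m, 80% at SD 22 m and 54% at SD 30 m.

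**The case against.** **H2b is a controlled half of Aim 2.** A reader might infer that duration is judged wholly by before-after change. The documents do not support that: H2b is randomised, both arms follow the same test schedule, and a shared repeat-test gain cancels. This stands. What H2b does not do is address growth after 4WK (step 5).

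**No repeat-test gain is documented.** A reader might infer that such gains are being credited to training. Neither document reports one, and zero is possible. The H2a intervals start at 4WK, after the first repeat test, so later gains may be smaller. Participants are 6 months to 5 years post stroke and not in physical therapy, which limits drift. The claim is only that any such gain could not be separated out.

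**H2a keeps its level.** It states that walking capacity will rise within HIT, and the test of that statement is valid. A reader might take the table in step 3 as an inflated type I error. It instead shows how often a true rise unrelated to training would be significant and open to misattribution.

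**MAT is an imperfect reference.** MAT also trains. Its target starts at 40% of heart rate reserve and rises by 5% every 2 weeks up to 60%: (60 − 40)/5 = 4 steps, so it can still be rising until about week 8. The between-arm increment therefore measures HIT-specific extra gain. This stands, and it argues against making that increment a condition for H2a. With 20 per arm, SD 22 m and an equal 3, 5 or 10 m repeat-test gain, requiring only a positive estimate would still pass about 8%, 15% and 37% of the time. Requiring significance would pass only about 2.5% of the time if longer training truly added 15 m in both arms.

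**The design is stated openly.** The 12-week assignment is explicit, and the Protocol elsewhere speaks of a time course.

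**Conclusion.** The concern holds in a limited form. There is no randomised comparison of HIT durations. The contrasts setting 12 weeks against 4 and 8 weeks are uncontrolled, and the hypothesised increase in benefit over MAT has no named test. The last gap rests on the documents alone and needs no assumption about repeat testing.

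The size of any misattribution is unknown. Over an assumed 3 to 10 m per interval, the chance of a significant rise without any training gain runs from 9% to 51% at SD 22 m and from 5% to 19% at SD 40 m. Both the gain and the SD are assumptions, and so is carrying an undiminished gain into the third and fourth tests.

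A reader might extend this to the primary result. That would be wrong: PRE to 4WK is tested between arms. The point concerns what Aim 2 may conclude.

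**What to change.** 1. In the Protocol (Hypothesis Testing, Aim 2) and the SAP (Hypothesis 2), prespecify the HIT-minus-MAT contrasts for 4WK to 8WK and for 8WK to 12WK, from the model already defined, as the test of increasing benefit over MAT. Report each with its estimate and 95% CI.
2. Report the MAT change beside every HIT change over the same interval.
3. Describe the H2a increments as an uncontrolled time course within one 12-week programme. Do not make the between-arm contrast a condition for H2a.
4. Reword the Background sentence on comparing durations to match.
5. State that these contrasts for secondary outcomes join the set under false discovery rate control.

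The cost is wording and two contrasts from a model already to be fitted, with no new visits or participants. The change should be dated before outcome analysis; otherwise the contrasts should be labelled post hoc. There are two drawbacks. The between-arm increment has an SE about 1.4 times larger. Because MAT also trains and its intensity target rises, it captures the extra gain specific to HIT and not the whole effect of longer training. That whole effect would need randomisation to duration with equal testing, which this trial cannot now supply.

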We propose a 3-site, 2-arm randomized controlled trial with blinded outcome assessment, stratified blocked randomization and an active control group (MAT) based on current best practice recommendations (Fig 4). Fifty persons with residual gait impairment >6 months post stroke will be recruited, consented, screened and randomized to either locomotor HIT or locomotor MAT. Treatment sessions will be time-matched between groups at 45 minutes, 3x/week for 12 weeks. Walking function, aerobic fitness and quality of life will be assessed by blinded raters at baseline (**PRE**) and after 4, 8 and 12 weeks of training (**4WK [primary endpoint], 8WK, 12WK**). Outcome measures will include: walking capacity (6-Minute Walk Test, *primary outcome measure*), gait speed (10-Meter Walk Test), aerobic fitness (ventilatory threshold & $VO_{2\text{ peak}}$), metabolic cost of gait, daily walking activity and quality of life (Stroke Impact Scale).

Recruitment

As in previous studies, recruitment will utilize a multimodal approach, including: 1) Continuous outreach to regional therapists and physicians; 2) Outreach to stroke support groups; 3)

[figure not shown]
Advertisements in newspapers, magazines, social media, physician offices and therapy clinics; 4) Existing databases of local stroke survivors interested in participating in research; 5) Screening medical records for potentially eligible participants. This initial identification of potential participants via medical records will only be used by study staff at UC or KUMC. UD study staff will not recruit using medical records.

Clinician referrals can be done in two ways: 1) the clinicians may provide the study team contact information to the potential participant; 2) if the potential participant verbally approves, the clinician can give the study team their name and contact information. Screening medical records for potentially eligible participants (by UC or KUMC study staff) will involve searching for cases of stroke and assessing other eligibility criteria in the electronic medical records system and databases of local hospitals and clinics, as in our previous UC IRB approved studies (e.g. 2013-7676, 2016-1916). We are requesting a HIPAA waiver for this purpose, as in our previous studies. For any potential participants who are identified solely by medical record review, we will only initiate a call to the participant if they have had a clinical encounter with one of the study investigators. Otherwise, we will initiate contact by mailing the participant an IRB approved flier (with the envelope addressed to "Current Resident") or by emailing an IRB approved flier to the email address(es) listed in their medical records (with the email address blind carbon copied).

For persons interested in participating, we will further explain the study, confirm initial eligibility and perform informed consent. After a research staff member explains the purpose of study and the consent, potential participants will be given the option to wait at least 24 hours to decide if they want to participate. During this consenting process, the potential participant will be provided a copy of the consent form. Standardized questions will be asked to ensure that the potential participant understands the study before consenting. HIPAA authorization will also be obtained as part of the consent process.

Figure 4. Study design

Informed consent

Spanish-speaking participants may be enrolled in the trial, if a site reports that Spanish-speaking individuals have expressed interest in participating. In this case, an approved Spanish-language version of the site's informed consent document will be used during the informed consent process. The consent process will be conducted as described in the previous paragraph. However, an official medical interpreter will be present during the consent process to interpret from English to Spanish and Spanish to English. A Spanish-speaking team member or medical interpreter will also be available during the study visits.

Eligibility criteria (Table 3) are based on our research experience, previous studies,^{33,50,51,54,69,76,77,81,82,98-101,141} and exercise guidelines^{6,142} and will maximize safety while balancing internal & external validity.¹⁴³

Table 3. Eligibility Criteria

Inclusion Criteria	Exclusion Criteria

1) Age 40-80 years
 
2) Single stroke for which participant sought treatment, experienced 6 months to 5 years prior to study entry
 
3) Walking speed <1.0 m/s on the 10 meter walk test^{21,57}
 
4) Able to walk 10m over ground with assistive devices as needed and no continuous physical assistance from another person (guarding and intermittent assistance for loss of balance allowed)³³
 
5) Able to walk 3 minutes on the treadmill at $\geq 0.13\text{m/s}$ (0.3 mph) (treadmill screening test)^{142,144}
 
6) Stable cardiovascular condition (AHA class B,¹⁴² allowing for aerobic capacity <6 METs)
 
7) Able to communicate with investigators, follow a 2-step command and correctly answer consent comprehension questions
	
1) Exercise testing uninterpretable for ischemia or arrhythmia (e.g. resting ECG abnormality that makes an exercise ECG uninterpretable for ischemia,¹⁴² and no other recent (within the past year) clinical testing to rule out these conditions).
 
2) Evidence of significant arrhythmia or myocardial ischemia on treadmill ECG graded exercise test¹⁴² in the absence of recent (within the past year) more definitive clinical testing (e.g. stress nuclear imaging) with a negative result.
 
3) Hospitalization for cardiac or pulmonary disease within past 3 months
 
4) Implanted pacemaker or defibrillator
 
5) Significant ataxia or neglect (score of 2 on NIH stroke scale item 7 or 11)¹⁴⁵
 
6) Severe lower limb spasticity (Ashworth >2)¹⁴⁶
 
7) Recent history (<3 months) of illicit drug or alcohol abuse or significant mental illness
 
8) Major post-stroke depression (Patient Health Questionnaire [PHQ-9] ≥ 10)¹⁴⁷ in the absence of depression management by a health care provider
 
9) Currently participating in physical therapy or another interventional study
 
10) Recent botulinum toxin injection to the paretic lower limb (<3 months) or planning to have botulinum toxin injections
 
11) Foot drop or lower limb joint instability without adequate stabilizing device, as assessed by a study staff physical therapist
 
12) Clinically significant neurologic disorder other than stroke or unable to walk outside the home prior to stroke
 
13) Other significant medical condition likely to limit improvement or jeopardize safety, (e.g. joint contracture, gait limited by pain), as assessed by a study staff physical therapist
 
14) Pregnancy
 
15) Previous exposure to fast treadmill walking (>3 cumulative hours) during clinical or research therapy in the past year


Screening and Baseline Assessment

After informed consent, participants will undergo screening and baseline assessment to confirm eligibility and to obtain baseline characteristics and potential cofactors. This testing may include: a medical record review (possibly including clinical radiography¹⁵⁹), a history & physical assessment (including pre-stroke functional status, stroke severity,¹⁴⁵ motor impairment,^{155,156} gait^{57,144} and balance^{154,157,158} testing), cognitive testing,¹⁵⁴ depression screening,¹⁴⁷ a treadmill screening test¹⁴⁴ and a stroke-specific treadmill ECG graded exercise stress test.¹⁴⁸ Female participants will also be asked about the possibility of pregnancy and will agree (as part of the informed consent process) to notify research staff if they have any reason to think they might be pregnant during the study. In this case, study activities would continue only after a urine pregnancy test is done and found to be negative.

Stress testing will be performed according to published guidelines^{127,137-139} by trained, experienced exercise testing laboratory staff at each of the sites. Assistance will be provided as needed from a licensed physical therapist or physical therapist assistant on the study team. Participants will wear a harness secured to an overhead support system for safety in case of loss of balance. ECG and vitals will be monitored. Participants will perform a maximal effort, graded treadmill exercise test to volitional fatigue. Treadmill speed will begin below the participant's fastest safe speed from the treadmill screening test. Increases in speed and/or grade will be used to gradually increase the workload until peak exercise capacity is reached. Test termination criteria will include participant request to stop at volitional fatigue, severe gait instability, or according to published guidelines.^{127,137-139}

Participants will be verbally notified about the results of their stress test. If they are disqualified from further participation in the study based on the results, they will also be given the option to have the results sent to their physician.

Blinded Outcome Testing

Outcome testing will be administered by licensed physical therapists or physical therapist assistants who are blinded to group randomization. Testing will occur before intervention (PRE) and after approximately 4, 8 and 12 weeks of training (4WK [*primary endpoint*], 8WK, 12WK). Each testing session will last approximately 2 hours and may include the following measures:

- Walking capacity testing (*6-minute walk test, primary outcome measure*) involves walking back and forth around two cones, using assistive devices, orthotics, guarding and rest breaks as needed.¹⁴⁸ The distance that the participant is able to walk in six minutes is recorded.
- Walking speed testing (*10-meter walk test*) will be performed with a stopwatch and/or a commercially available electronic walkway.^{146,147} Participants will walk down a hallway and/or electronic walkway, using assistive devices, orthotics and guarding as needed. Each test may be performed twice at comfortable speed and twice as fast as possible.
- Aerobic capacity testing involves respiratory gas measurement (VO₂ and VCO₂) by having the participant breathe through a facemask during an exercise test. This testing will use the same exercise protocol as the stress test above and may be performed simultaneously with the stress test. Peak aerobic capacity is defined as the highest VO₂ measurement achieved during the test. After finishing this test and a rest period, participants may complete a verification phase to help determine whether maximum physiologic capacity (a true VO₂-max) was reached.¹⁵¹ During this verification phase, the participant would be asked to walk as fast as possible for approximately 3 minutes. The treadmill screening test may be repeated at each testing time point to inform speed selection for aerobic capacity testing.
- The metabolic cost of gait is measured by the oxygen consumption rate (VO₂) during gait, with adjustment for walking speed and resting VO₂.⁷⁹ The metabolic cost of gait will be assessed with treadmill walking at approximately the average speed recorded during the 6-minute walk test.
- Daily walking activity assessment involves wearing an activity monitor continuously during waking hours for ≥ 3 days and possibly recording sleep/wake times.¹⁵²⁻¹⁵⁵ The monitor will be worn on the non-paretic leg.
- The Stroke and Aphasia Quality of Life Scale,^{157,158} Stroke Impact Scale,¹³⁸ EQ-5D and Patient Health Questionnaire¹⁴⁷ are reliable and valid self-report quantitative surveys that include questions about quality of life. One or more of these questionnaires will be used.
- The Global Rating of Change (GROC)¹⁵⁹ is a questionnaire that assesses overall impressions of change in health status from the perspective of the participant. The GROC is a 15 point ordinal scale with -7 indicating "a very great deal worse," 0 indicating "no change," and +7 indicating "a very great deal better". The GROC is not applicable at baseline testing because it measures change only.

Heart rate data may also be recorded during the above testing. If there are any issues with data capture (e.g. equipment malfunction), it is possible that participants could be asked to repeat individual tests as long as it would still be possible to obtain quality data without increasing risk to the participant.

Randomization

Participants will be enrolled after PRE testing and randomized to either HIT or MAT. Randomization will be stratified by site and by baseline walking speed (<0.4 , ≥ 0.4 m/s), to help ensure that groups are balanced within sites and on this critical prognostic factor.^{149,150} Within each stratum, we will randomize in *block sizes of 2 or 4*. Block size will be *randomly permuted* to prevent personnel from being able to predict the last randomization within a block.

Training Intervention Protocols

Common features between protocols. Participants in both groups will be asked to perform 36 training sessions over approximately 12 weeks, with repeated outcome testing after each [12 session / 4 week] block. Target training frequency will be 3 sessions per week. Both groups will train for approximately 45 minutes per session, v.5, 16Mar2021

using orthotic & assistive devices and handrail balance support on the treadmill as needed.¹⁴⁴ Each session will include a 3 minute warm up, 10 min overground training with guarding from a physical therapist, 20 min treadmill training wearing a harness for fall protection, another 10 min overground training and a 2 min cool down. Target heart rates (HRs) will be based on the peak HR from exercise testing, to account for β -blocker medications.¹⁴⁴

Locomotor high-intensity interval training (HIT). This protocol was developed and refined in our preliminary studies. It involves repeated bursts of walking at speeds up to the participant's fastest safe speed, alternated with recovery periods of slower walking or rest. During overground HIT, burst speed is increased using visual feedback about the distance covered during each burst and encouragement to increase distance. During treadmill HIT, speed is systematically progressed throughout each session based on participant performance criteria and heart rate response.^{9,81,82} Target average HR for each session is approximately 85% HR_{peak} (~70% HR reserve [HRR]).

Locomotor moderate-intensity aerobic training (MAT). Similar to our pilot randomized controlled trial,⁹ this protocol will follow the widely reported training regimen of Macko et al,^{33,46,50,51,60-62,144,215,216} used as the basis for current post-stroke exercise guidelines.^{6,8} The only adjustment for this study will be the addition of overground MAT¹⁰⁹ to match the training modes and duration of locomotor HIT. During both treadmill and overground MAT, speed will be continuously adjusted to maintain an initial target HR of 40 \pm 5% heart rate reserve (HRR), progressing by 5% HRR every 2 weeks up to 60% HRR, as tolerated.¹⁴⁴

[figure not shown]
Intervention fidelity measures

Integrity of the training protocol may be assessed by the following measures:

- Adherence will be measured by the number of training sessions attended
- Aerobic intensity will be measured by training heart rates. Heart rate data may be collected by a heart rate transmitter worn around the chest (e.g. Polar H7), an ECG, a pulse oximeter and/or manual palpation. Heart rate data may be processed using an iPod (or similar) application (e.g. FitDigits iCardio).
- Anaerobic intensity may be measured by *blood lactate concentration* after the treadmill training portion of one or more sessions, using a finger stick and a point-of-care blood lactate analyzer. Blood lactate accumulation is a key feature of vigorous training intensity that provides a mechanistic basis for expected benefits over moderate intensity. Our preliminary data confirmed that among persons with chronic stroke, the anaerobic threshold still occurs almost exactly at the 60% HR reserve transition point between moderate and vigorous intensity.¹³⁶ Further, we demonstrated that our treadmill HIT protocol elicits a consistent and robust lactate response in this population, which is significantly greater than the null effect elicited by MAT ($p<0.001$; Fig 5). In animal and healthy adult studies, increased blood lactate has been shown to drive skeletal muscle mitochondrial adaptations that increase aerobic capacity,¹⁶⁶ to upregulate neurotrophins that facilitate brain plasticity¹⁶⁷ and to predict greater motor learning when paired with skill practice.¹⁶⁸
- Neuromotor intensity may be measured by *treadmill and over ground training speeds* each session.
- Repetition of practice may be measured by *step counts* during each session, using an activity monitor on the non-paretic leg.^{27,34,35,169,170}

Concurrent outside interventions

To test for other between-group differences during the intervention period that could explain differences in outcomes, we may also assess the following measures:

- Concurrent walking practice may be measured by *step counts outside of training sessions*. Participants would be asked to take an activity monitor home to wear during waking hours throughout study participation.¹⁷¹
- Concurrent therapy may be measured by *any changes in medications* and the *number of sessions of outside therapy (e.g. speech & occupational therapy)*.¹⁵⁶

E.2. Data Analysis and Data Monitoring

General approach

[figure not shown]
The REDCap® web-based system²¹⁷ will be used for data entry and data monitoring. All baseline variables and data on intervention fidelity and concurrent outside interventions will be compared between groups with t-tests and X². The primary analysis will follow *intent-to-treat* methods and any missing data will be handled with the method of maximum likelihood, assuming that patterns of missingness do not violate the missing at random assumption.²¹⁸

